4.2.1 When and How to Discontinue Treatment

Treatment will be discontinued and the subject may be withdrawn from the study prior to completion due to any of the following reasons:

1. The subject experiences greater than 3 typical seizures during the 3 day course of TMS treatment or they experience a single atypical seizure (atypical duration or severity for the patient) as judged by study neurologist.
2. The subject experiences a worsening of depressive symptoms by the discretion of the study psychiatrist.
3. The subject withdraws consent.
4. The subject is not able to tolerate TMS (as assessed by self-reported side effects).
5. The subject does not adhere to protocol requirements.

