7.1 Statistical Methods

The study will be closely monitored for safety parameters with stopping rules as defined in Section 8.7. At the conclusion of the study, baseline demographics and clinical characteristics will be summarized with means, proportions and associated standard deviations. For safety, occurrence rates of SAE (seizures or hospitalizations) will be estimated and exact binomial confidence intervals will be formed. Very few if any are expected in this small study. The SAFTEE scale will be compared before and after TMS with independent t-tests based on the individual changes from baseline. The study completion rates will be estimated and compared to the target rate of 80% using exact tests for binomial data.

The secondary outcomes will be measured before and after treatment using dense-array EEG biomarkers and depression scores along with test results during functional MRI and EEG. Paired t-tests will be used to compare *change* in depression severity, memory, executive functioning, quality of life, and social cognition from baseline to endpoint. MRI patterns of activation will be analyzed. Analysis of variance for repeated measures will be used to test task and neuropsychological testing results.

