7.3 Subject Population(s) for Analysis

The patients successfully initiating the trial will be the analysis population to the safety outcomes. The patients completing the TMS will be the population for the secondary outcomes.

8 Safety and Adverse Events

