- Hospitalization or prolonged hospitalization for diagnostic or elective surgical procedures for a preexisting condition. Surgery should **not** be reported as an outcome of an adverse event if the purpose of the surgery was elective or diagnostic and the outcome was uneventful.
- Hospitalization or prolonged hospitalization required to allow efficacy measurement for the study.
- Hospitalization or prolonged hospitalization for therapy of the target disease of the study, unless it is a worsening or increase in frequency of hospital admissions as judged by the clinical investigator.

8.2 Notification and Recording of Self Harm as Indicated by the MINI and/or QIDS

Subjects will complete a series of assessments several times during their participation in the study. Two of the assessments, the MINI and the QIDS, are validated measures of depression. On the QIDS, participants are asked to select a response that best describes how they have been feeling in the past seven days. Item 12 asks about "Thoughts of Death or Suicide." This particular question will be reviewed by study personnel each time the subject completes the QIDS. Each time a subject responds positively to this question by selecting a 2 ("I think of suicide or death several times a week for several minutes.") or a 3 ("I think of suicide or death several times a day in some detail, or I have made specific plans for suicide or have actually tried to take my life.") the following procedure will be followed by study personnel:

- 1) Administer the Columbia Suicide Severity Rating Scale (C-SSRS).
- 2) Notify the study psychiatrist and an appropriate clinician (if needed) for assessment.
- 3) In REDcap, under **Safety Reporting**, document that the subject gave this answer, when the answer was given, and the clinician(s) notified.
- 4) The notified clinician may follow up with the subject and take appropriate action according to the unique situation. If the answer is given after exposure to TMS, treatment may be discontinued or reduced.

The MINI contains a module that asks subjects about suicidal ideation and behavior in the past month. The six items in this module have a possible point total of 33. A score above 6 corresponds to a "Moderate" current risk of suicide, while a score of 10 or above indicates a "High" current suicide risk. In cases where a subject reports a score of 6 or greater, the above procedure will be followed by study personnel.

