8.7 Stopping Rules

Study safety will be monitored by the co-PIs .The study will be stopped at if the following endpoints are reached:

1. If recruitment for the study is not feasible
 - a. no recruitment after 1 year
 - b. > 4 drop outs due to any reason (80% feasibility)
2. If TMS is deemed unsafe to patients with epilepsy

- a. > 3 patients with increase in baseline seizure frequency
- b. > 3 patients with significant worsening of depression
- c. > 3 patients with significant side effects of TMS other than seizures

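### Worsening depression and suicidal ideation are handled as safety matters during the trial, but section 7.1 plans no patient-level safety analysis of either

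*Combined protocol and SAP*

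**What the plan says.** Worsening depression is treated as a possible harm in several places.

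- Section 4.2.1, item 2, discontinues treatment, with possible withdrawal from the study, if "The subject experiences a worsening of depressive symptoms by the discretion of the study psychiatrist".
- Section 8.7 stops the study, under the heading of TMS being unsafe, at "> 3 patients with significant worsening of depression".
- Section 8.2 requires staff, after any QIDS item 12 answer of 2 or 3, to administer the C-SSRS, notify the psychiatrist and "document that the subject gave this answer, when the answer was given, and the clinician(s) notified". If the answer comes after TMS exposure, treatment may be discontinued or reduced.
- Section 8.1 records worsening of a preexisting condition as an adverse event. It keeps depressive symptoms as one of two event types still reported after day 30.

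The analyses are narrower. For safety, section 7.1 says that "occurrence rates of SAE (seizures or hospitalizations) will be estimated and exact binomial confidence intervals will be formed" and that "The SAFTEE scale will be compared before and after TMS with independent t-tests based on the individual changes from baseline". Depression severity enters as a paired t-test of change "in depression severity, memory, executive functioning, quality of life, and social cognition from baseline to endpoint". Section 3.2, item 4, also correlates depression change with EEG biomarkers.

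Section 7.3 sets two populations: "The patients successfully initiating the trial will be the analysis population to the safety outcomes", whereas "The patients completing the TMS will be the population for the secondary outcomes".

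**The concern.** Safety is the primary objective of this uncontrolled study, and its participants are depressed patients with epilepsy. A mean change answers whether the group moved on average. It does not say how many patients deteriorated, which is what rule 2b counts.

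Two mechanisms operate. A patient who completes TMS and worsens is netted against those who improve. A patient whose treatment is ended under 4.2.1 for worsening leaves the TMS-completer population, and so leaves the only depression comparison. The SAE rate does not catch either patient unless there is an admission, because 7.1 restricts it to seizures or hospitalizations. The SAFTEE comparison is itself a group mean. Section 7.1 plans no summary of non-serious adverse events, of item 12, or of the C-SSRS. The final analysis could therefore show a significant antidepressant effect and give no rate for patients who became more depressed or more suicidal.

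**Working it through.** **Inputs from the plan.** n = 20; two-sided alpha 0.05, power 0.90 and detectable difference 0.764 SD of the changes (7.2); study stop at more than 3 patients worsened or more than 4 drop-outs (8.7); completion target 80% (Specific Aim 1); exact binomial intervals as the safety method (7.1). The QIDS changes and true worsening rates below are assumed.

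**1. The plan's own figure.** For a paired t-test, df = 19, critical t = 2.093 and noncentrality = 0.764 × √20 = 3.417. The noncentral t gives power 0.8997, and solving for power 0.90 gives 0.7645 SD. The stated 0.764 reproduces, but it concerns a mean only. If changes are normal and the mean improvement is exactly 0.764 SD, the share of patients changing in the worse direction is Φ(-0.764) = 0.222, or 20 × 0.222 = 4.4 patients. Some of that is ordinary fluctuation, so it is not a harm rate. It shows how little the mean reveals about individuals.

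**2. Netting (all 20 complete TMS; 17 change by -5 QIDS points, 3 by +6).**

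- Mean = (17 × -5 + 3 × 6)/20 = -67/20 = -3.35.
- Sum of squares = 17 × 25 + 3 × 36 = 533. Variance = (533 - 20 × 3.35²)/19 = 308.55/19 = 16.24, so SD = 4.03.
- t = -3.35/(4.03/√20) = -3.72, p = 0.0015 in favour of benefit.
- Worsened: 3/20 = 15%. The Clopper-Pearson 90% limits are the 5% quantile of Beta(3, 18) = 0.042 and the 95% quantile of Beta(4, 17) = 0.344.
- Three is not more than 3, so rule 2b is not met.

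**3. Exclusion (17 patients spread normally about -5, SD 2.98; 3 others worsen by 5).** One of the 17 also rises, by 0.7 point.

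- All 20 analysed: mean -3.5, SD 4.57, t = -3.42, p = 0.003.
- The 3 discontinued for worsening and dropped under 7.3: mean -5.0, SD 2.98, t = -6.92, p < 0.0001.
- Completion is 17/20 = 85%, above the 80% target. Neither the drop-out rule (more than 4) nor rule 2b (more than 3, if only these 3 are judged significant) is met.

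Removing the patients who worsened raises the estimated benefit from 3.5 to 5.0 points.

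**4. Is the stopping rule a substitute?** With X the number of patients worsening significantly among 20, the rule stays silent if X ≤ 3:

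| True worsening rate | P(X ≤ 3) | P(X > 3) |
|---|---|---|
| 5% | 0.984 | 0.016 |
| 10% | 0.867 | 0.133 |
| 15% | 0.648 | 0.352 |
| 20% | 0.411 | 0.589 |

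At 15%, the study finishes without meeting the rule about 65% of the time, with up to 3 worsened patients and no planned rate for them.

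**The case against.** The best defence is that the protocol does watch for this harm. Worsening is an adverse event under 8.1, all adverse events are recorded under 8.4, depressive symptoms remain reportable after day 30, rule 2b is a per-patient count, and an admitted patient enters the SAE rate. A patient taken off TMS also lowers the completion rate. All of this stands. A reader might infer that patients made worse would be absent from the results altogether, and the documents do not support that. What is missing is a planned analysis that shows them.

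A reader might also infer that suicidal ideation stops treatment and the study. It does not. Section 8.2 says only that treatment may be discontinued or reduced, and no rule in 8.7 names ideation. Nor is the t-test the only use of depression change, since the biomarker correlation uses it too, although that correlation does not count deteriorating patients. A scenario with 4 of 20 worsening significantly would meet rule 2b and stop the study, so it cannot be called unnoticed harm.

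Three limits remain. The illustrations rest on assumed values, and any mean can hide a minority. It matters here because the protocol itself classes that minority as a safety signal. Rule 2b does not define significant worsening, and the study monitoring plan (Attachment E) is not in the text reviewed, so a definition or tabulation there cannot be excluded. Finally, this is a small pilot with no summary of non-serious adverse events at all, so depression is one instance of a wider gap. It is the instance that the protocol's own stopping rules single out.

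**Conclusion.** The point holds in this form: section 7.1 contains no patient-level safety analysis of worsening depression or emergent suicidal ideation, and the TMS-completer restriction in 7.3 adds exclusion to averaging. Under the assumed values, a 15% worsening rate (90% exact CI 4% to 34%) coexists with p = 0.0015 for benefit and no rule 2b stop. The 0.65 chance that rule 2b stays silent at a true rate of 15% assumes 20 treated patients with independent outcomes. The conclusion rests on reading 7.1 as the complete list of planned analyses and its parenthesis as limiting the SAE rate to seizures and hospitalizations. It does not imply that TMS worsens depression, or that events would go unrecorded. The plan should be changed, because the gap bears on the primary safety question and QIDS is already collected before treatment and at Visits 5 to 9.

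**What to change.** Add to the safety analyses in 7.1, on the safety population of 7.3 (all who initiate, including those whose treatment is ended early, using the follow-up in 4.3.2), the number and proportion of patients with an exact binomial confidence interval for:

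1. Significant worsening of depression as counted for rule 2b, with the sponsor stating beforehand the criterion it uses for that count. Beside it, give the number with any QIDS increase from the pre-TMS score, visit by visit, as a description only, since small rises partly reflect ordinary fluctuation.
2. A post-TMS QIDS item 12 score of 2 or 3 that is higher than the patient's pre-TMS score. Requiring a rise, rather than a pre-TMS score below 2, matters because section 4.1 excludes only scores above 2. A patient may enrol at 2, and a move to 3 must count. List the C-SSRS results that 8.2 triggers.

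Name which pre-TMS QIDS is used (it is given at Visits 1b and 3), and report how many patients have no post-TMS QIDS. Keep the mean-change t-test as the secondary analysis.

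The cost is a few table rows, one listing, and advance agreement on the rule 2b criterion. No new assessment is needed and no clinical rule changes. Intervals will be wide at n = 20: even 0 of 20 leaves a two-sided 95% upper limit of 16.8%. The safety table will look less favourable if patients worsen.

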6.1 Visit 1a: Initial Screening by Neurologist – Pre-enrollment

- Patient will review and sign informed consent.
- Initial screening will be done by a board-certified neurologist (, Visit 1a). Patient's history and physical will be taken, medications will be reviewed, seizure log, MOCA will be performed if time permits. All incomplete assessments may be done at Visit 1b.
- Subject will receive seizure log and instructions for its use.

6.2 *Visit 1b: Initial Screening by Psychiatrist – Pre-enrollment*

- Subsequent evaluation will be done by board-certified psychiatrist and research assistant Visit 1b). If the subject is unable to complete the full screening during Visit 1a, he or she may be scheduled for a second screening appointment with study psychiatrist and research assistant. At that time, diagnosis of medication-resistant depression will be confirmed; the MINI, QIDS, SAFTEE, PANAS MRI safety, TASS and ATHF will be performed. Seizure log data will be obtained.
- If time permits, Visit 2 procedures can be done at Visit 1b.

6.3 *Visit 2: Imaging and Baseline Neuropsychological Testing – Pre Enrollment*

- Patient will be report to the Advanced Imaging Center for MRI. MRI will last approximately one hour.
- After MRI is complete, patient will be brought to the EEG lab . A dense-array EEG will be conducted which will take approximately one hour.
- Patient will do neuropsychological and social-cognition testing, which will last approximately 2 hours. (QOLIE-31, RBANS and MAC-S)
- If time permits, TMS motor threshold may be done at Visit 2, so long as TMS treatment is scheduled to begin within one week. Otherwise, TMS motor threshold will be done at Visit 3.

6.4 *Visit 3: Enrollment and first day of TMS treatment*

- Patient will be brought to DHMC by their proxy for the first day of TMS treatment.
- Research staff will administer the QIDS, SAFTEE, and PANAS. Data will be obtained from the patient's seizure log.

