6.8 Visit 7: 1-month follow up

- 1 month after visit 5 (+/- 2 weeks), the patient will return to DHMC for a follow up with the study neurologist for history and physical, and medication review. Seizure log will be reviewed.
- The patient will have the SAFTEE, QIDS, and MoCA administered by research staff.
- Neuropsychological testing (QOLIE-31, MAC-S, RBANS),
- Dense-array EEG test will be conducted.

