6.10 Visit 9: 6-month follow up

- 6 months after Visit 5 (+/- 4 weeks) the patient will return to DHMC for a follow up with the study neurologist, coordinator, and psychiatrist.
- Research staff will administer the MoCA, QIDS, and SAFTEE. Seizure log will be reviewed.
- Neuropsychological testing (QOLIE-31, MAC-S, RBANS) will be done by research staff.
- Medication review will be done with patient or through review of electronic medical record.
- A dense-array EEG test will be conducted, which may include EEG tasks.

7 Statistical Plan

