7.2 Sample Size Determination

For the primary safety outcomes, we consider the expected upper limit of a one-sided 90% exact confidence interval for the proportion with an SAE based on a sample size of 20. If the underlying rate is 0.05, the upper limit is 0.131. This increases to 0.145 if the underlying rate is 0.10.

For the secondary outcomes comparing baseline to endpoint depression measurements, a two-sided paired t-test with a significance level of 0.05 and a power of 0.90 can detect a difference of .764 standard deviations of the changes from baseline.

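### The repeated-measures ANOVA for three-visit neuropsychological data has no missing-visit rule; a prespecified mixed model would recover part of the precision that complete-case analysis loses

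*Combined protocol and SAP*

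**What the plan says.** The Combined protocol and SAP schedules the three scales at three visits:

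- Visit 2, baseline (section 6.3): "Patient will do neuropsychological and social-cognition testing, which will last approximately 2 hours. (QOLIE-31, RBANS and MAC-S".
- Visit 7, one month (section 6.8): "Neuropsychological testing (QOLIE-31, MAC-S, RBANS".
- Visit 9, six months (section 6.10): "Neuropsychological testing (QOLIE-31, MAC-S, RBANS) will be done by research staff".

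Section 7.1 names two analyses for overlapping content. One is the ANOVA: "Analysis of variance for repeated measures will be used to test task and neuropsychological testing results". The other is a set of simple before-after tests: "Paired t-tests will be used to compare *change* in depression severity, memory, executive functioning, quality of life, and social cognition from baseline to endpoint". The endpoint visit is not named. Nothing is said about software, covariance, sphericity correction or missed visits, and the plan has no separate missing-data section.

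Section 7.3 sets the population: "The patients completing the TMS will be the population for the secondary outcomes". Section 4.3.2 continues follow-up of withdrawn subjects, but the time points it lists end at three months. Section 7.2 gives a detectable difference for the paired t-test on depression only, with no allowance for drop-out. No power figure is given for the ANOVA.

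**The concern.** A classical repeated-measures ANOVA needs a score at every visit. A patient seen at one month but not at six would contribute nothing, and the Visit 7 score already collected would go unused. In a single-arm study of 20, a few such losses matter.

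There are two further problems. Complete cases may differ from the patients who miss a visit, and with no control arm any such selection goes straight into the estimated change. The classical F test also relies on sphericity, which is doubtful when the gaps between visits are unequal (baseline, one month, six months).

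**Working it through.** **1. The plan's own figure.** Inputs from section 7.2: "a two-sided paired t-test with a significance level of 0.05 and a power of 0.90", and n = 20. The two-sided paired t-test has n − 1 degrees of freedom and noncentrality d√n. Solving for 90% power gives d = 0.7645; power at 0.764 is 0.8997. The stated 0.764 SD reproduces, and it is the full-sample figure.

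**2. What a smaller n costs, same formula.**

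| n | power at 0.764 SD | detectable change at 90% power |
|---|---|---|
| 20 | 0.900 | 0.764 SD |
| 18 | 0.863 | 0.811 SD |
| 16 | 0.815 | 0.868 SD |
| 14 | 0.753 | 0.938 SD |

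These are paired-t values, used as a scale for precision. They are not power figures for the ANOVA.

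**3. Complete cases under assumed missingness.** Let m be the chance of missing each follow-up visit, independently, with baseline always observed. Expected complete cases are 20(1 − m)².

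- m = 0.10: 20 × 0.81 = 16.2 patients. Scores collected: 20 + 2 × 18 = 56. Scores used by a complete-case ANOVA: 3 × 16.2 = 48.6.
- m = 0.20: 20 × 0.64 = 12.8 patients. Scores collected: 20 + 2 × 16 = 52. Scores used: 3 × 12.8 = 38.4.

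**4. Effective n of a mixed model for the Visit 9 change.** Sum the information over the four missingness patterns and invert to get the variance of the estimated change. Effective n is then 2(1 − ρ)/variance, with unit variance at each visit and equal correlation ρ, treated as known. Expected counts (all three scores; Visits 2 and 7 only; Visits 2 and 9 only; Visit 2 only) are 16.2, 1.8, 1.8 and 0.2 at m = 0.10, and 12.8, 3.2, 3.2 and 0.8 at m = 0.20. For ρ from 0.4 to 0.8:

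| m | complete cases | paired t-test, Visit 2 to Visit 9 | mixed model, effective n |
|---|---|---|---|
| 0.10 | 16.2 | 18 | 18.5 to 18.7 |
| 0.20 | 12.8 | 16 | 16.8 to 17.2 |

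The standard error, in SDs of change, is 1/√n. At m = 0.10 it falls from 1/√16.2 = 0.248 to 1/√18.5 = 0.232, about 6%. At m = 0.20 it falls from 1/√12.8 = 0.280 to 1/√17 = 0.243, about 13%. Neither reaches the full-sample 1/√20 = 0.224.

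**5. Simulated power of the overall visit test.** There were 600 runs per setting, n = 20, correlation 0.6, and both follow-up changes equal to 0.764 SD of change. Monte Carlo error is 1 to 2 points. The fitted mixed model was a random-intercept model matching the simulated truth, so an unstructured fit would gain somewhat less.

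| missingness | complete-case ANOVA | mixed model, F test |
|---|---|---|
| 10% at each follow-up visit | 0.86 | 0.93 |
| 20% at each follow-up visit | 0.76 | 0.90 |
| 20% at Visit 9 only, depending on the Visit 7 score | 0.90 | 0.91 |

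In the last setting the mean estimated Visit 9 change was 0.685 for complete cases and 0.690 for the mixed model, against a true 0.683. That set-up shows no visible bias in either.

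**6. Small-sample correction.** With an unstructured covariance and complete data, an uncorrected Wald chi-square test of the two changes rejects above 5.991. By Hotelling's T², (n − 2)/[2(n − 1)] times the statistic follows F(2, n − 2). The true type I error is about 8.5% at n = 20 and 9.5% at n = 16, against a nominal 5%.

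**The case against.** The strongest reply is that the plan nowhere says incomplete patients are dropped. A reader might infer that every patient with one missed visit is deleted, but section 7.1 names no implementation, and the same phrase can cover a likelihood-based repeated-measures model. This stands as a limit on the claim: deletion follows from the classical form. It does not remove the gap, because the choice is left open.

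Second, the paired t-tests in section 7.1 already cover memory and quality of life. If the endpoint is Visit 9, a patient who missed only Visit 7 is kept. If it is Visit 7, a patient who missed only Visit 9 is kept. This also stands. Against the paired test, the mixed model's gain for the Visit 9 change is small: about 18.5 against 18, or 17 against 16.

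Third, a reader might take the move from 0.76 to 0.87 SD as the price of the ANOVA, or think that a mixed model restores all 20 patients at no cost. The calculation supports neither. Part of the loss is data never collected. The model brings its own assumptions, and it needs a degrees-of-freedom correction at this sample size. Choosing compound symmetry would bring sphericity back, and it would not in general reproduce the paired comparison when data are complete.

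Fourth, a reader might infer that patients who do badly will miss Visit 9, so that results will look too good. The documents give no evidence on who misses visits. The limit of four drop-outs in section 8.7 is a feasibility stopping rule, not a missed-visit rate. If absence depends on scores never observed, a mixed model does not cure it.

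**Conclusion.** The point holds as a cheap improvement. For three-visit neuropsychological data the plan names a method whose ordinary form uses complete cases only, and it gives no missing-visit rule. Under assumed independent missingness of 10% (20%) per follow-up visit, complete cases number about 16 (13) of 20, against an effective n of about 18.5 (17) for the Visit 9 change from a mixed model. The loss is partly recovered. The gain in simulated power was 7 to 14 points when both follow-up visits could be missed, and about 1 point when only Visit 9 was.

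These sizes rest on assumed missingness rates, an equal-correlation structure and, for the effective n, a known covariance. All 20 patients are taken to be in the analysis population; the completer restriction in section 7.3 could lower that under either method. The direction of any selection bias cannot be settled from the documents. The consequence is confined to the precision and possible bias of secondary results in a single-arm pilot; the primary safety and feasibility conclusions do not depend on it.

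**What to change.** In section 7.1, replace the repeated-measures ANOVA for these scales with a linear mixed model on all observed scores:

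- visit as a categorical effect, with baseline included as an outcome;
- one prespecified unstructured covariance, with a named fallback if it does not converge;
- Kenward-Roger degrees of freedom;
- Visit 7 and Visit 9 changes from baseline estimated from the model, with confidence intervals.

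State that this model also supplies the baseline-to-endpoint comparisons for the same scales now assigned to paired t-tests, and name the endpoint visit. State the missing-at-random assumption and add one simple sensitivity analysis, for example shifting the missing scores by a range of fixed amounts.

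Including patients who did not complete TMS is a separate change to section 7.3. It can be reported as a supportive analysis, using the one-month data that section 4.3.2 already plans to seek from withdrawn subjects.

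The cost is a few sentences of plan text and standard software, with no new data. The downside is reliance on missing at random and on a covariance estimated from about 20 patients.
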